6.1. Eribulin – Expected toxicities

In a completed Phase 3 trial, E7389-G000-305, eribulin (1.4 mg/m² on Days 1 and 8 of a 3-week cycle) was compared with treatment of the physician's choice (TPC; any cytotoxic or hormonal agent) in subjects heavily pre-treated for locally advanced or metastatic breast cancer. Grade 3 or 4 eribulin-related AEs were asthenia/fatigue (7.6%), neutropenia (44%), and peripheral neuropathy (8.4%). Twelve percent of eribulin-treated subjects and 7% of TPC-treated subjects experienced treatment-related SAEs.

Refer to Section 5.2 of the Investigator's Brochure for complete details on toxicity in previous clinical trials conducted with eribulin.

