6.2. Eribulin - Toxicity Management

Subjects should be carefully monitored for toxicity. If Grade 3 or 4 toxicities are present, then treatment should be delayed to allow for recovery (see instructions for dose delay below). If toxicities recur, the dose of eribulin should be reduced. In the setting of neutropenia, growth factor support may be added instead of a dose reduction at time of first occurrence of neutropenia at the discretion of the investigator. Once the dose of eribulin is reduced, it may not be increased at a later date. Dose adjustment recommendations for eribulin are shown in Table 1.

Eribulin Dose Levels

Starting dose	1.4 mg/m²
1 st dose reduction	1.1 mg/m ²
2 nd dose reduction	0.7 mg/m ²

Table 1: Dose adjustment recommendations for eribulin

Adverse reaction/Toxicity^a	Grade/Details	Eribulin dose modification
ANC	< 500 cells/mm ³ lasting > 7 days in the previous cycle without use of growth factors	Hold eribulin until recovery to grade ≤ 2. Eribulin may be resumed at the same dose with growth factor support, or it may be reduced by one dose level, per investigator discretion.
	< 500 cells/mm ³ lasting > 7 days in the previous cycle despite use of growth factors	Hold eribulin until recovery to grade ≤ 2, and reduce by 1 dose level.
	<1000 /mm ³ with fever or infection without use of growth factors	Hold eribulin until recovery to grade ≤ 2. Eribulin may be resumed at the same dose with growth factor support, or it may be reduced by one dose level, per investigator discretion.
	<1000 /mm ³ with fever or infection despite use of growth factors	Hold eribulin until recovery to grade ≤ 2, and reduce by 1 dose level.
	<1000 /mm ³ without fever or infection without use of growth factors	Hold eribulin until recovery to grade ≤ 2 then resume at the same dose with growth factor support. If uncomplicated neutropenia lasting < 1 week (<1000 /mm ³ without fever or infection) occurs/recurs despite growth factor support, then hold eribulin until recovery to grade ≤ 2 . Eribulin may be then be resumed at the same dose with growth factor support, or it may be reduced by one dose level, per investigator discretion.

		If uncomplicated neutropenia lasting > 1 week (<1000 /mm ³ without fever or infection) occurs/recurs despite growth factor support, then hold eribulin until recovery to grade ≤ 2 and reduce by 1 dose level.
Platelets	Grade 2	Hold eribulin until recovery to grade 1

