	Grade 3	Hold eribulin until recovery to grade 1 then reduce by 1 dose level.
	Grade 4	Hold eribulin until recovery to grade 1 then reduce by 1 dose level.
Anemia	Grade 4	Hold eribulin until recovery to grade ≤ 2 then reduce by 1 dose level. PRBC transfusions are permitted to treat anemia.
Peripheral neuropathy	Grade 2	For intolerable (as determined by physician and patient) grade 2, decrease chemotherapy by one dose level.
	Grade 3	Hold eribulin until recovery to grade ≤ 2 then reduce by 1 dose level.
	Grade 4	Treatment discontinuation.
Non-hematologic toxicity	Grade 3, first occurrence	Hold eribulin until recovery to grade ≤ 2. Maximize supportive care measures. If symptom recovery occurs within 1 week, then eribulin may be resumed at the same dose if deemed appropriate by the investigator, otherwise, reduce by 1 dose level.
	Recurrent grade 3, or any grade 4 toxicity	Hold eribulin until recovery to grade ≤ 2 then reduce by 1 dose level.
Recurrence of any Grade 3 or 4 event despite reduction to 0.7 mg/m ² , or persistent grade 3 or 4 toxicity lasting more than 3 weeks despite maximal supportive measures		Treatment discontinuation

ANC = absolute neutrophil count a: Toxicities graded in accordance with National Cancer Institute Common Toxicity Criteria for Adverse Events, version 4.0, Appendix 5
		

Instructions for Dose Delay

Criteria to continue treatment

- Absolute Neutrophil Count $\geq 1000/\text{mm}^3$ or $\geq 1.0 \times 10^9/\text{L}$
- Platelet Count $\geq 75,000/\text{mm}^3$ or $\geq 75 \times 10^9/\text{L}$
- Non-hematologic toxicity \leq grade 2

Eribulin will NOT be administered if any of the following values are present on Day 1 or 8 prior to treatment administration:

- Absolute Neutrophil Count $< 1,000/\text{mm}^3$ or $< 1.0 \times 10^9/\text{L}$
- Platelet Count $< 75,000/\text{mm}^3$ or $< 75 \times 10^9/\text{L}$
- Non-hematologic toxicity CTCAE Grade 3 or 4

If the dose of eribulin cannot be administered as planned due to treatment-related toxicity, the dose should be delayed according to the following instructions:

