11. ADVERSE EVENT REPORTING REQUIREMENTS

11.1. Definitions

11.1.1. Adverse Event (AE)

An adverse event (AE) is any undesirable sign, symptom or medical condition or experience that develops or worsens in severity after starting the first dose of study treatment or any procedure specified in the protocol, even if the event is not considered to be related to the study.

Abnormal laboratory values or diagnostic test results constitute adverse events only if they induce clinical signs or symptoms or require treatment or further diagnostic tests.

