14.3. Safety analysis

All patients who receive at least one dose of the study regimens will be included in the assessment of adverse events (full analysis population). Adverse event information for the two cohorts will be combined. Safety data that will be evaluated include AEs, clinical laboratory results, vital signs, and ECGs. Abnormal laboratory values will be flagged.

Adverse event information will be collected from the time the subject signs the ICF until resolution or for 30 days after the subject's last study visit, whichever comes first. Treatment-emergent AEs (TEAEs) will be analyzed. Adverse events will be regarded as TEAEs if they started on or after the date and time of administration of the first dose of study treatment or if they were present before the administration of the first dose of study treatment and increased in severity during the study. Treatment-emergent peripheral neuropathy will be followed until resolution or until the start of another anticancer therapy post treatment, whichever occurs first.

Adverse events will be graded using CTCAE v 4.0 (Appendix 5). Investigators will collect all CTCAE grades for all AEs (to assess both increasing and decreasing severity). Events will be summarized by frequency and percentage.

The incidence of TEAEs and relatedness to study treatment will be summarized. Although an adverse event may be reported more than once for a subject, that subject will be counted only one time in the incidence count for that adverse event term by the highest CTCAE grade (in the summary by CTCAE grade) and by the closest causal relationship to study treatment (in the summary by relatedness to study treatment).

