3.9.2. Reporting Procedures

DF/HCC Sponsor: is responsible for ensuring that clear documentation is available in the medical record and/or regulatory documents to describe all protocol exceptions, deviations

and violations. The DF/HCC Sponsor will also be responsible for ensuring that all protocol violations/deviations are promptly reported per DFCI IRB guidelines.

Participating Institutions: Protocol deviations require prospective approval from the DFCI IRB. The Participating Institution must submit the deviation request to the Coordinating Center who will then submit the deviation request to the DFCI IRB. Upon DFCI IRB approval the deviation is submitted to the Participating Institution IRB, per institutional policy. A copy of the Participating Institution's IRB report and determination will be forwarded to the Coordinating Center within 10 business days after the original submission.

All protocol violations must be sent to the Coordinating Center in a timely manner.

Coordinating Center: Upon receipt of the violation/deviation report from the Participating Institution, the Coordinating Center will submit the report to the DF/HCC Sponsor for review. Subsequently, the Participating Institution's IRB violation/deviation report will be submitted to the DFCI IRB for review per DFCI IRB reporting guidelines.

3.10. **Safety Assessments and Toxicity Monitoring**

The study teams at all participating institutions are responsible for protecting the safety, rights and well-being of study participants. Recording and reporting of adverse events that occur during the course of a study help ensure the continuing safety of study participants.

All participants receiving investigational agents and/or other protocol mandated treatment will be evaluated for safety. The safety parameters include all laboratory tests and hematological abnormalities, physical examination findings, and spontaneous reports of adverse events reported by participants. All toxicities encountered during the study will be evaluated according to the NCI criteria specified in the protocol. Life-threatening toxicities must be reported immediately to the DF/HCC Sponsor via the Coordinating Center.

Additional safety assessments and toxicity monitoring will be outlined in the protocol.

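### Section 11.1.1 can keep asymptomatic Grade 3/4 laboratory toxicity out of the adverse event table, and Section 14.3 plans no graded laboratory table that would show it

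*Combined protocol and SAP*

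**What the plan says.** - **Section 11.1.1 (definition).** "Abnormal laboratory values or diagnostic test results constitute adverse events only if they induce clinical signs or symptoms or require treatment or further diagnostic tests". There are three triggers: signs or symptoms, treatment, and further diagnostic tests. The last two are not defined.
- **Section 14.3 (analysis).** Each patient is counted once per adverse event term, at the highest CTCAE grade, among TEAEs. Laboratory results are named as a safety component beside AEs, vital signs and ECGs, but the only instruction for them is "Abnormal laboratory values will be flagged".
- **Section 6.2 and Table 1 (actions on counts).** For ANC below 500 lasting more than 7 days without growth factors, the dose is held until recovery and then: "Eribulin may be resumed at the same dose with growth factor support, or it may be reduced by one dose level, per investigator discretion". Grade 2 platelets mean a hold; Grade 3 or 4 platelets mean a hold and then a reduction. Anaemia has a row for Grade 4 only.
- **Dose-delay instructions in 6.2.** "Eribulin will NOT be administered if any of the following values are present on Day 1 or 8 prior to treatment administration". The list that follows covers ANC, platelets and non-haematologic Grade 3 or 4 toxicity. Haemoglobin is not on it.
- **Section 10.5 and Table 4.** Haematology and chemistry are drawn at Screening, on Days 1 and 8 of every cycle, and at End-of-Treatment.
- **Appendix 9, Section 3.10.** "The safety parameters include all laboratory tests and hematological abnormalities, physical examination findings, and spontaneous reports of adverse events reported by participants".

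**The concern.** Safety and tolerability of eribulin is a stated secondary objective (Section 1.3), analysed with the two cohorts combined. The only graded safety summary in Section 14.3 is the TEAE table, and a laboratory event that fails Section 11.1.1 never reaches it, whatever its grade. Because the triggers are undefined, two sites can classify the same count differently.

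Haematologic toxicity is where this matters most. Section 6.1 gives neutropenia as the most frequent of the Grade 3 or 4 eribulin-related events it lists, at 44% in the cited Phase 3 trial. AE status also decides whether a Grade 4 count enters the reporting table in Section 11.2.

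**Working it through.** The plan states no figure on this point, so there is none to reproduce. The check has two parts.

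**1. Applying the three triggers to asymptomatic events**

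| Event | Action in Section 6.2 | Treatment? | Further tests? | AE under 11.1.1? |
|---|---|---|---|---|
| Grade 3 anaemia, no transfusion | No Table 1 row; not in the dose-delay list | No | No; next count already scheduled | No |
| Platelets Grade 2 to 4 | Hold; at Grade 3 or 4 also reduce | None named | Only if a recount qualifies | Unclear |
| ANC <500 for >7 days, no prior growth factor; growth factor chosen | Hold, same dose with growth factor | Yes | Not needed | Yes |
| Same event; dose reduction chosen | Hold, reduce one level | Only if a dose change counts | Only if a recount qualifies | Unclear |
| ANC <1000 without fever or infection, no prior growth factor | Table 1: hold, "then resume at the same dose with growth factor support" | Yes | Not needed | Yes |

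ANC below 1000 with fever or infection is an AE through its signs, whichever option is chosen.

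Two qualifications apply:
- The opening text of Section 6.2 calls for a delay at Grade 3 or 4 toxicity in general. If that covers anaemia, the first row becomes unclear as well. Table 1 and the dose-delay list point the other way, and these passages should be reconciled.
- The same opening text says that "growth factor support may be added instead of a dose reduction at time of first occurrence of neutropenia at the discretion of the investigator". This is wider than the Table 1 cell in the last row.

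**2. Direction and possible size**

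The rule can remove laboratory events from the AE table but cannot add any, so an error can only be downward. The share removed, f, is not in the documents and cannot be derived from them.

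Inputs: n = 45 + 45 = 90 (Section 1.1); assumed true Grade 3/4 rate p = 44%, borrowed from Section 6.1, with 30% and 60% as a range; f assumed at 0%, 10%, 25% and 50%.

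Formula: tabulated count = 90 × p × (1 − f), rounded to whole patients. For p = 44%: 90 × 0.44 = 39.6, about 40 patients.

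| p | f = 0% | f = 10% | f = 25% | f = 50% |
|---|---|---|---|---|
| 30% | 27/90 = 30.0% | 24/90 = 26.7% | 20/90 = 22.2% | 14/90 = 15.6% |
| 44% | 40/90 = 44.4% | 36/90 = 40.0% | 30/90 = 33.3% | 20/90 = 22.2% |
| 60% | 54/90 = 60.0% | 49/90 = 54.4% | 40/90 = 44.4% | 27/90 = 30.0% |

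Exact 90% intervals for the 44% row: 35.5–53.7%, 31.3–49.2%, 25.1–42.4% and 15.2–30.6%.

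For scale, the approximate 90% half-width at 44% is 1.645 × √(0.44 × 0.56 / 90) = 0.086. The shift is 0.44 × f, which equals 0.086 at f = 0.086 / 0.44, about 20%. A 10% omission (4.4 points) is inside sampling error; a 25% omission (11 points) is outside it. This shows what f would have to be for the effect to matter, not what f is.

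**The case against.** The strongest case against rests on the third trigger. ANC below 1000 on Day 1 or 8 blocks dosing, and every ANC row in Table 1 requires a hold until recovery. A blocked Day 8 dose may still be given by Day 15, which needs a count outside the Day 1/Day 8 schedule. If that count is a further diagnostic test, dose-blocking neutropenia is an AE under either management option, and f is near zero for it.

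This stands as a possible reading, but the protocol does not adopt it. If the Day 8 dose is omitted instead, the next calendar count is the routine Day 1 of the following cycle. If routine recounts qualified, the restriction in 11.1.1 would exclude almost nothing. Nor does the reading reach Grade 3 anaemia that leads to no hold.

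Four stronger conclusions are tempting, and the documents do not support them:
- *AE status of severe neutropenia generally turns on growth factor versus dose reduction.* The split is confined mainly to ANC below 500 for more than 7 days without growth factors. Febrile or infected cases are AEs either way, the Table 1 cell for first uncomplicated ANC below 1000 writes in growth factor, and patients in the rows despite growth factor are already treated.
- *Nothing in the plan could recover the events.* Laboratory results are a separate component of the safety evaluation, and the values are collected. What is missing is a prespecified graded summary.
- *Appendix 9 contradicts 11.1.1.* It lists laboratory abnormalities as safety parameters beside AE reports. It does not say that each one is an AE.
- *Eribulin would look safer against 44%.* No such comparison is planned, and 44% is itself an AE rate from a trial whose AE definition is not given here.

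**Conclusion.** The concern holds as a risk of undercount in the TEAE table. It is clear for asymptomatic, untransfused Grade 3 anaemia, taking Table 1 and the dose-delay list as they stand. It depends on interpretation for asymptomatic low platelets and for ANC below 500 lasting more than 7 days managed by hold and dose reduction.

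The direction is certain: any error lowers the reported rate. The size is unknown. At an assumed true rate of 44% the table could show anything from about 44% (nothing omitted) to about 22% (half omitted), and the omitted shares are assumptions without a source. A reader might infer that the reported haematologic rate is in fact biased low; the documents support only that it can be.

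The primary endpoint, ORR, is unaffected. The point is still worth acting on, because safety is a stated objective and the remedy uses data already collected.

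**What to change.** 1. **Section 14.3.** Replace the flagging sentence with a prespecified table of worst post-baseline CTCAE grade per patient for ANC, platelets, haemoglobin, AST, ALT and bilirubin. Derive it from the Table 4 values, with patients who received at least one dose as denominator, and show it beside the TEAE table.
2. **Section 11.1.1.** State that a laboratory abnormality is recorded as an AE if it is CTCAE Grade 3 or higher, or if it leads to a held, delayed, omitted or reduced dose or to discontinuation, in addition to the present triggers.

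The first change alone makes the laboratory rates independent of how sites read 11.1.1. The second makes the TEAE table consistent across sites. Neither alters a dosing or management rule.

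The cost is one table, more AE recording at sites, and higher reported haematologic toxicity rates. Newly recorded Grade 4 events would also fall under the Section 11.2 timetable unless the protocol lists them as expected and exempt from expedited reporting, so the sponsor should settle that in the same amendment.

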11.1.2. Serious adverse event (SAE)

A serious adverse event (SAE) is any adverse event, occurring at any dose and regardless of causality that:

- Results in death
- Is life-threatening. Life-threatening means that the person was at immediate risk of death from the reaction as it occurred, i.e., it does not include a reaction which hypothetically might have caused death had it occurred in a more severe form.
- Requires or prolongs inpatient hospitalization (i.e., the event required at least a 24-hour hospitalization or prolonged a hospitalization beyond the expected length of stay). Hospitalization admissions and/or surgical operations scheduled to occur during the study period, but planned prior to study entry are not considered SAEs if the illness or disease existed before the person was enrolled in the trial, provided that it did not deteriorate in an unexpected manner during the trial (e.g., surgery performed earlier than planned).
- Results in persistent or significant disability/incapacity. Disability is defined as a substantial disruption of a person's ability to conduct normal life functions.
- Is a congenital anomaly or birth defect; or
- Is an important medical event when, based upon appropriate medical judgment, it may jeopardize the participant and require medical or surgical intervention to prevent one of the outcomes listed above. Examples of such medical events include allergic bronchospasm requiring intensive treatment in an emergency room or at home; blood dyscrasias or convulsions that do not result in inpatient hospitalization, or the development of drug dependency or drug abuse.

Events **not** considered to be serious adverse events are hospitalizations for:

- routine treatment or monitoring of the studied indication, not associated with any deterioration in condition, or for elective procedures
- elective or pre-planned treatment for a pre-existing condition that did not worsen
- emergency outpatient treatment for an event not fulfilling the serious criteria outlined above and not resulting in inpatient admission
- respite care

11.1.3. Expectedness

Adverse events can be 'Expected' or 'Unexpected.'

Expected adverse event

Expected adverse events are those that have been previously identified as resulting from administration of the agent. For the purposes of this study, an adverse event is considered expected when it appears in the current adverse event list, the Investigator's Brochure, the package insert or is included in the informed consent document as a potential risk.

Refer to Section 6.1 for a description of expected adverse events associated with eribulin.

Unexpected adverse event

For the purposes of this study, an adverse event is considered unexpected when it varies in nature, intensity or frequency from information provided in the current adverse event list, the Investigator's Brochure, the package insert or when it is not included in the informed consent document as a potential risk.

11.1.4 Attribution

Attribution is the relationship between an adverse event or serious adverse event and the study treatment. Attribution will be assigned as follows:

- Definite – The AE is clearly related to the study treatment.
- Probable – The AE is likely related to the study treatment.
- Possible – The AE may be related to the study treatment.
- Unlikely - The AE is doubtfully related to the study treatment.
- Unrelated - The AE is clearly NOT related to the study treatment.

Procedures for AE and SAE Recording and Reporting

Participating investigators will assess the occurrence of AEs and SAEs at all participant evaluation time points during the study.

All AEs and SAEs whether reported by the participant, discovered during questioning, directly observed, or detected by physical examination, laboratory test or other means, will be recorded in the participant's medical record and on the appropriate study-specific case report forms.

The descriptions and grading scales found in the revised NCI Common Terminology Criteria for Adverse Events (CTCAE) version 4.0 will be utilized for AE reporting. All appropriate treatment areas should have access to a copy of the CTCAE version 4.0.

A copy of the CTCAE version 4.0 can be downloaded from the CTEP website at:

http://ctep.cancer.gov/protocolDevelopment/electronic_applications/ctc.htm.

Reporting Requirements

Each investigative site will be responsible to report SAEs that occur at that institution to the Overall Primary Investigator, [name] and to their own Institutional IRB. DF/HCC sites will report to [name], and the DFCI/HCC IRB. Complete reporting instructions are described below.

Reporting to the Study Sponsor

Serious Adverse Event Reporting

Serious adverse events that occur after the initial dose of study treatment, during treatment, or within 30 days of the last dose of treatment must be reported to the DF/HCC Overall Principal Investigator on the local institutional SAE form. This includes events meeting the following criteria:

- Grade 2 (moderate) and Grade 3 (severe) Events – Only events that are unexpected and possibly, probably or definitely related/associated with the intervention.
- All Grade 4 (life-threatening or disabling) Events – Unless expected AND specifically listed in the protocol as not requiring reporting.
- All Grade 5 (fatal) Events – When the participant is enrolled and actively participating in the trial OR when the event occurs within 30 days of the last study intervention.

Note: If the participant is in long term follow up, report the death at the time of continuing review.

Participating investigators must report each serious adverse event to the DF/HCC Overall Principal Investigator within 24 business hours of learning of the occurrence. In the event that the participating investigator does not become aware of the serious adverse event immediately (e.g., participant sought treatment elsewhere), the participating investigator is to report the event within 24 business hours after learning of it and document the time of his or her first awareness of the adverse event. Report serious adverse events by telephone, email or facsimile to:

[name] MPH
[contact]
[contact]
[contact]

Within the following 24-48 hours, the participating investigator must provide follow-up information on the serious adverse event. Follow-up information should describe whether the event has resolved or continues, if and how the event was treated, and whether the participant will continue or discontinue study participation.

Non-Serious Adverse Event Reporting

Non-serious adverse events will be reported to the DF/HCC Overall Principal Investigator on the toxicity Case Report Forms.

